Confidence in our estimates is enhanced because they are based on data from our recently completed factorial trial of CR and AT using the same patient population and primary outcome. The chosen sample size has adequate power for the primary and secondary aims and QOL. The effect of CR+AT on peak VO₂ was 110.8 ml/min (7.6% relative effect) with a square root of the mean square error for the ANCOVA model being 107.5. To have 90% power to detect a relative effect due to RT of 5.6% (absolute difference of 82.0 ml/min) in peak VO₂ at the 0.05 two-sided level of significance, the study requires 38 evaluable participants per group. In our recent trial, the retention rate was excellent (93%), similar to our previously published trials in HFpEF. To allow for up to 11% loss to follow-up, a total of 42 subjects per group (84 total) will be randomized. In our recently completed study, we observed a 7.4 cm² decrease in thigh muscle area measured by MRI in the CR+AT vs. control group. The square root of the mean square error was 5.98 using analysis of covariance. With 76 evaluable subjects we will have 80% power to detect if the decrease in muscle mass is reduced by 53% (e.g. a difference of 3.9 cm²). In our study of older, non-HF participants, RT had an effect of this magnitude on muscle retention during CR.(198). We will confirm muscle retention with DXA measurement of total lean mass. In our recently completed study; we observed a 2.2 kg decrease (3.2% relative effect) (square root mean squared error of 28.47) providing 80% power to detect a 2.8% relative effect of RT. This sample size also allows adequate power for the secondary aim, mitochondrial function. In our pilot study, RT increased respiratory control ratio (RCR) from 2.78 to 7.23 (160% increase; mean square error of 6.372). The sample size provides 80% power to detect a 60% increase in RCR. It also provides 80% power to detect a 10% relative difference in the KCCQ QOL score. The sample size also provides adequate power to detect increases in confirmatory measures of exercise capacity. In our recent study, we observed a 35.4%, 13.8%, and 13.9% increase in the AT+CR vs. control group in exercise time, VO₂ reserve, and six-minute walk distance respectively. The sample size provides 90% power to detect a 10%, 8%, and 6% increase in exercise time, VO₂ reserve, and six-minute walk, respectively. We will also have 80% power to detect partial correlations as low as 0.30 at the 0.05 two-sided level of significance to examine independent relationships with peak VO₂.

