Mitochondrial Mechanisms for Skeletal Muscle Loss, a phenomenon related to reduced peak VO₂ in HFrEF(3) but never examined in HFpEF, will be assessed by using: 1) expression of Bax, ICE, p53, Fas receptor protein, and cyclophilin D as indices of programmed cell death;(171) 2) Bcl-2 as an index of protection against apoptosis; and 3) calcium retention capacity and H₂O₂ emission in PmFBs as indices of susceptibility to opening of the mitochondrial permeability transition pore and mitochondrial failure.(6; 173)

Physical Activity will be assessed using two accelerometers, the Actigraph GT3X+ and the Lifecorder EX. The Actigraph monitor is a small device worn on the non-dominant wrist, and the Lifecorder monitors is a small device worn on the right hip, attached to the waistband. Both monitors assess variables related to physical activity: energy expenditure, steps, and physical activity duration, intensity, and frequency. Participants will wear both devices for 7 continuous days during baseline and follow-up testing to assess changes in physical activity pre to post intervention. There are no risks associated with wearing an activity monitor.

Study visit timeline.

Table 3. Assessment Timeline	Visit code	SV	BV1	BV2	BV3	Interv.	FV1	FV2	FV3
Activity/assessment	Week number					0-20			
Informed consent, screening, demographics, echocardiogram/Doppler, dietary interview		X							
Physical exam, medical history, medication review		X					X		
RMR, Blood draw, questionnaires, Exercise test			X				X		
SPPB, Muscle strength, DXA & MRI scans				X				X	
Muscle biopsy					X				X
Randomization and dietary education					X				

Analytical Plan

The trial is a 2-arm, randomized, parallel design to test the effect of adding RT to the regimen of CR+AT shown as most beneficial in our recent trial. Peak VO₂ (ml/min) will be the primary outcome measure using an intention-to-treat analysis. Analyses will be conducted using analysis of covariance (ANCOVA) with baseline peak VO₂, age and gender as predefined covariates. Similar analyses will be done for the secondary outcomes, skeletal muscle mass and mitochondrial function, QOL, and other outcomes. Partial correlation analysis adjusting for age and gender will be done to correlate changes in peak VO₂ with the other key outcomes of interest (muscle mass, mitochondrial function, and QOL).

Data Management

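### The 80% power claimed for a partial correlation of 0.30 is not reached with the plan's 76 evaluable participants; power is about 74–75%

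*Combined protocol and SAP*

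**What the plan says.** The Sample Size section of the combined protocol and SAP bases the primary calculation on completers: "the study requires 38 evaluable participants per group", which is 76 in total. Randomisation is set higher to cover attrition: "To allow for up to 11% loss to follow-up", "a total of 42 subjects per group (84 total) will be randomized". The thigh muscle calculation names the same evaluable number: "With 76 evaluable subjects we will have 80% power".

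The paragraph closes with the correlation claim, for which no N is given: "We will also have 80% power to detect partial correlations as low as 0.30 at the 0.05 two-sided level of significance".

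The Analytical Plan defines the analysis: "Partial correlation analysis adjusting for age and gender", relating changes in peak VO₂ to muscle mass, mitochondrial function and QOL. This serves the third secondary hypothesis under Objectives, that the gain in peak VO₂ with resistance training is related to better muscle mass and mitochondrial function.

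**The concern.** A correlation between changes needs baseline and 20-week values on both variables. The relevant N is therefore the evaluable number, not the number randomised. A correlation of 0.30 usually needs about 85 observations for 80% power at two-sided 0.05, which is already more than this trial randomises, so the claim looked too favourable at 76.

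This sentence is the only power statement for the correlation part of the third secondary hypothesis (the QOL part has its own KCCQ figure). If the power is overstated, a null correlation between change in peak VO₂ and change in muscle mass or mitochondrial function would count as stronger evidence against the proposed mechanism than the design can supply.

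**Working it through.** **Inputs**
- Target partial correlation r = 0.30, two-sided α = 0.05, stated power 80% (Sample Size).
- Evaluable N = 2 × 38 = 76; randomised N = 84 (Sample Size).
- Covariates removed: k = 2, age and gender (Analytical Plan).
- Retention in the group's recent trial: 93% (Sample Size), giving 84 × 0.93 ≈ 78.

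**Formulas (Fisher's z)**
- Power = Φ(atanh(r) × √(N − 3 − k) − 1.960); the opposite tail is negligible.
- Smallest r with 80% power = tanh((1.960 + 0.842) / √(N − 3 − k)).
- N for 80% power = ((1.960 + 0.842) / atanh(r))² + 3 + k.
- atanh(0.30) = 0.3095.

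**Where the stated 80% can be found**
- N = 84, k = 0: 0.3095 × √81 = 2.786; 2.786 − 1.960 = 0.826; power 79.6%.
- N = 84, k = 2: 0.3095 × √79 = 2.751; 2.751 − 1.960 = 0.791; power 78.6%.

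The stated figure is close to what all 84 randomised participants would give with no losses. That this is its source is an inference, because the sentence does not say.

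**At the plan's evaluable number**
- N = 76, k = 2: 0.3095 × √71 = 2.608; 2.608 − 1.960 = 0.648; power 74.2%.
- Smallest r with 80% power: tanh(2.802 / √71) = tanh(0.3325) = 0.321.
- N needed for r = 0.30: (2.802 / 0.3095)² = 81.9; adding 3 + 2 gives 86.9, so 87. With no covariates it is 84.9, so 85.

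**Summary, with a simulation of the t test under bivariate normality (2 million draws)**

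| N | k | Fisher z | Simulated | Smallest r with 80% power (Fisher z) |
|---|---|---|---|---|
| 76 | 2 | 74.2% | 74.8% | 0.321 |
| 76 | 0 | 75.3% | 75.9% | 0.317 |
| 78 | 2 | 75.3% | 75.9% | 0.317 |
| 84 | 2 | 78.6% | 79.1% | 0.305 |
| 84 | 0 | 79.6% | 80.1% | 0.302 |

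**Other readings at N = 76, k = 2**
- A bias-corrected Fisher z gives 74.7%.
- A noncentral t calculation that treats the regressors as fixed gives 77.2%, the most favourable two-sided result.
- A one-sided test gives 83.2%, but the sentence specifies a two-sided level.

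**Comparison with another figure in the paragraph.** The thigh muscle statement does hold at 76: 3.9 / (5.98 × √(2/38)) = 2.843; 2.843 − 1.960 = 0.883; power 81.1%, against 80% stated. The correlation sentence does not fit that same N.

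**The case against.** The strongest reply is that the sentence names neither its N nor its method. With a fixed-regressor noncentral t calculation, power is 77.2% at 76 (smallest r with 80% power 0.310) and 81.3% at 84, so 80% is right for the randomised number. On this view the defect is an unstated N rather than a wrong sum. It is fair that the range across methods at 76 is 74–77%. However, both variables here are observed changes, neither fixed by design, so the random-regressor figures of 74–75% suit the analysis better. The favourable method still misses 80% at 76, and at 78 (78.3%). Using 84 assumes no losses, against the allowance made in the same paragraph.

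A second point is that 76 is not a ceiling: the 93% retention cited would leave about 78. That stands, but it lifts power only to 75.3% by Fisher's z. In the other direction, correlations with mitochondrial measures need two usable biopsies, and those with thigh area need two usable scans. The documents give no rate for missing pairs, so that loss cannot be sized. As an assumption only, 70 to 76 usable pairs would give about 70% to 74%.

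Third, the gap is small, concerns a secondary association, and a null result should be read from its confidence interval. All of that is fair and limits the importance of the point, but it does not make the stated figure correct.

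**Conclusion.** The claim does not hold as written. With 76 evaluable participants and adjustment for age and gender, power for a partial correlation of 0.30 is about 74–75%, so the chance of missing it is about 26% (100 − 74.2) rather than 20%. The correlation detectable with 80% power is 0.32. No two-sided calculation tried at 76 or 78 reaches 80%.

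This rests on the plan's own evaluable number, its two named covariates, the two-sided 0.05 level and approximate bivariate normality of the changes. The primary sample size and the planned analysis are unaffected. It is a modest error in one stated design property and should be corrected.

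**What to change.** Replace the sentence in the Sample Size section with one that names its N and covariates, for example: *With 76 evaluable participants and adjustment for age and gender, there is 80% power at two-sided 0.05 for a partial correlation of 0.32 (about 74% power for 0.30).* Also name the method (Fisher's z), since the result shifts by up to 3 points with that choice.

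The cost is one sentence and a slightly less favourable figure. Neither the sample size nor the analysis changes.

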This is a randomized, controlled, single-blind clinical trial. After baseline assessments, 84 patients with HFpEF aged \geq 60 years will be randomly assigned to 1 of 2 groups: CR+AT or CR+AT+RT. Outcomes will be assessed in blinded fashion at baseline and after the 20week intervention. The primary outcome is peak VO₂ (in ml/min) by expired gas analysis during treadmill exercise to exhaustion. The secondary outcome of skeletal muscle mass will be measured by MRI and DXA. The secondary outcome of mitochondrial function will be assessed by respirometry, protein expression analyses, and enzyme activity assays on *vastus lateralis* muscle biopsy samples with RCR as a pre-planned, key outcome. Other measures will include: health-related QOL by the KCCQ instrument, SF-36, EuroQOL, and CES-D. SPPB; lower extremity strength and power by isokinetic dynamometer; muscle quality; 6-min walk distance; thigh composition and LV and arterial function by MRI; and LV diastolic function by echo-Doppler.

Setting

All study tests and procedures will be performed at Wake Forest School of Medicine and Wake Forest University Clinical Research Center. Testing labs include the Cardiac Ultrasound and Stress Testing lab, Clinical Research Unit, Geriatric Research Center, and the Center for Magnetic Resonance Imaging.

Subjects Selection Criteria

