2. Preserved Ejection Fraction $\geq 50\%$
3. LV diastolic dysfunction (\geq grade 1)
4. Age ≥ 60
5. BMI ≥ 28

Exclusion Criteria

- Medical
 - A. Valvular heart disease as the primary etiology of HF
 - B. Significant change in cardiac medication or HF symptoms < 6 weeks
 - C. Hospitalization or urgent care visit < 6 weeks
 - D. Uncontrolled hypertension
 - E. Uncontrolled diabetes
 - F. Evidence of significant COPD defined as either:
 - a. On continuous home oxygen therapy for COPD
 - b. Hospitalization for COPD in last 6 months
 - G. Recent or debilitating stroke
 - H. Cancer or other noncardiovascular conditions with life expectancy less than 2 years
 - I. Significant anemia (< 10 gms Hgb) (eligibility will be determined by CBC)
 - J. Significant renal insufficiency (eGFR < 30 ml/min/1.73 m²) (eligibility will be determined by comprehensive metabolic panel)
 - K. Pregnancy-women of child bearing potential are excluded from participation in this study.
- Psychiatric disease- uncontrolled major psychoses, depressions, dementia, or personality disorder
- Other
 - A. Plans to leave area within 1 year
 - B. Refuses informed consent
- Screening Echocardiogram
 - A. Left ventricular ejection fraction $< 50\%$
 - B. Significant valvular heart disease
- Exercise Test
 - A. Evidence of significant ischemia
 - B. Electrocardiogram: 1mm flat ST depression
 - C. Stopped exercising due to chest or leg claudication or any reason other than exhaustion/fatigue/dyspnea
 - D. Exercise SBP > 240 mmHg, DBP > 110 mmHg
 - E. Unstable hemodynamics or rhythm
 - F. Unwilling or unable to complete adequate exercise test
- Magnetic resonance imaging
 - A. Indwelling metal-containing prosthesis (orthopedic, valvular, other)
 - B. Pacemaker or defibrillator
 - C. History of welding occupation (ocular metal debris)
 - D. Uncontrollable claustrophobia
 - E. Any other contra-indication to MRI
- Thigh muscle biopsy
 - A. History of bleeding disorder
 - B. Current anticoagulation

- C. Contraindication to stopping aspirin for 1 week
- D. Allergy to topical anesthetic

Sample Size

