Short physical performance battery (SPPB). The SPPB is a measure of physical function that incorporates three components: usual gait speed measured over 4 meters, timed repeated chair rise, and standing balance with progressively narrow base of support. Each component is scored on a 0-4 scale and then summed to provide an overall score range of 0-12. We will evaluate the overall SPPB as well as each component. A change of 1 point in the overall SPPB score has been identified as representing a substantial change and 0.5 points as a small meaningful change.(172)

Lower extremity muscle strength will be assessed as maximal isokinetic knee extensor strength (Newton-meters, Nm) in both legs using an isokinetic dynamometer (Biodex®) with the participant seated and the hips and knee flexed at 90°. For consistency, seat height and depth will be recorded and the best of 2 trials will be selected. Test-retest reliability of knee extensor maximal voluntary contraction is high among older adults.(38; 189)

Hand grip strength will be measured in both hands using an adjustable grip strength dynamometer.(113) The participant will be seated with the elbow at 90 degrees. Two trials will be recorded for each hand.

Body composition will be measured by dual-energy x-ray absorptiometry (DXA, Hologic Delphi QDR).(100) Scans will be analyzed by a certified DXA technician experienced in body composition measures in older adults.(100) Whole body DXA estimates body and regional mass, lean mass, fat mass, and bone. Percent lean mass will be calculated as lean mass / total mass x 100. Total and appendicular skeletal muscle mass will be estimated using the Heymsfield method.(42) Precision of our DXA lean mass measurements is excellent (CV = 0.51%).

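### SPPB components are described for analysis only as 0-4 scores, although gait speed and chair rise are timed; analysing the timed values as well would recover lost power on a supportive outcome

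*Combined protocol and SAP*

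**What the plan says.** The SPPB paragraph (Outcome Measure(s)) lists the battery as "usual gait speed measured over 4 meters, timed repeated chair rise, and standing balance". The scoring rule follows: "Each component is scored on a 0-4 scale and then summed to provide an overall score range of 0-12". The analysis statement comes directly after it: "We will evaluate the overall SPPB as well as each component". The paragraph closes with thresholds for the total: "A change of 1 point in the overall SPPB score has been identified as representing a substantial change and 0.5 points as a small meaningful" change.

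The Design section places the battery among the other measures: "SPPB; lower extremity strength and power by isokinetic dynamometer; muscle quality; 6-min walk distance". The Analytical Plan specifies ANCOVA for peak VO2 with baseline value, age and gender as covariates, and says that other outcomes will be handled similarly. It does not say in what form the SPPB components enter. The Sample Size section makes no statement about the SPPB, and no baseline mean, SD or share at the maximum score is given anywhere.

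**The concern.** Two of the three components are measured on continuous scales and then cut into a few ordered categories with a cap. A patient who becomes faster without crossing a cut-point shows no change, and a patient already at 4 cannot show improvement. Both effects weaken a between-arm comparison even though the underlying measurement is available.

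Four of the six resistance exercises train the legs, so chair rise is a plausible place for a benefit of added resistance training to appear. If only the component scores are tested, a real difference in chair-rise time or gait speed may be reported as no difference on that component. If the wording was meant to cover raw values too, it leaves the choice between score and raw value to be made after the data are seen. One sentence resolves either case.

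**Working it through.** **The plan's own figure.** The Sample Size section gives a difference of 82.0 ml/min, a residual SD of 107.5, two-sided 0.05, 90% power and 38 evaluable per group. The normal formula gives n = 2 × (1.960 + 1.282)² × (107.5/82.0)² = 2 × 10.51 × 1.719 ≈ 36.1, so 37. With the noncentral t, power is 0.899 at 37 and 0.907 at 38. The stated 38 is reproduced and is used below. There is no SPPB figure to reproduce.

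**Inputs.**
- From the documents: 38 per arm, two-sided 5%, ANCOVA on the baseline value, component score 0-4.
- Assumed, because the documents are silent: pre-post correlation 0.75, share of patients at the top score at baseline, and the gain common to both arms (0 or 0.3 SD). Some common gain is plausible because both arms receive caloric restriction and aerobic training.

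**Effect size.** The difference detectable with 80% power is (1.960 + 0.842) × √(2/38) = 0.643 residual SD. With correlation 0.75 the residual SD is √(1 − 0.75²) = 0.661 of the raw SD, so this is 0.643 × 0.661 ≈ 0.425 raw SD. The simulation used 0.435, slightly more, to allow for the t distribution and the estimated covariate. Simulated power on the continuous measure was then about 80%.

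**Simulation.** Baseline and follow-up were drawn as bivariate normal and analysed by ANCOVA, first as continuous values and then after both were cut into score categories at the same cut-points. There were at least 4,000 runs per scenario, so the Monte Carlo standard error is at most √(0.25/4000) ≈ 0.8 percentage points.

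| Assumed share at top score at baseline | Power on the component score (0.3 SD common gain to none) |
|---|---|
| 10-20% | about 62-66% |
| 30% | about 57-62% |
| 50% | about 45-53% |
| 70% | about 30-40% |
| 85% | about 14-24% |

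**Sensitivity.** With five categories, no common gain and correlation varied from 0.6 to 0.8, score power was 64-71% with 20% at the top, 58-64% with 40%, 46-52% with 60% and 28-32% with 80%. The number of categories and the correlation matter little; the share at the top matters a great deal.

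**Reading the first row.** Power of 62-66% in place of 80% corresponds to an information ratio of ((1.960 + 0.305)/2.802)² ≈ 0.65 to ((1.960 + 0.412)/2.802)² ≈ 0.72. That is roughly what 25 to 27 patients per arm would give on the continuous measure (38 × 0.65 and 38 × 0.72). Most of this loss comes from the coarse categories, since few patients are at the cap in that row.

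**Scope.** The simulation models a single timed component. It gives no loss for the 0-12 total, which also contains balance.

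**The case against.** The strongest reply is that the wording is merely unspecific. The components are introduced as a speed and a timed task, so analysing each component could include raw values. That is fair as far as it goes: raw values are not excluded. But the sentence follows directly on the 0-4 scoring rule, and nothing in the Analytical Plan adds speed or time, so the scores remain the natural reading.

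A second reply is that little depends on it, and this largely stands. The SPPB is an unpowered supportive outcome. Six-minute walk distance is continuous and has its own statement (90% power for a 6% increase), and knee-extensor strength is recorded in Nm. A reader might infer that the SPPB is the trial's measure of physical function, so that an effect on function would be missed altogether. The Design section does not support that; an effect could be missed on the SPPB components only.

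A reader might also infer that the entry criteria push patients to the ceiling. Exclusions such as "Unwilling or unable to complete adequate exercise test" and "Stopped exercising due to chest or leg claudication or any reason other than exhaustion/fatigue/dyspnea", together with those for debilitating stroke and metal prostheses, lean that way. But no criterion uses the SPPB, gait speed or chair rise, the prosthesis exclusion is listed as an MRI contraindication, and a patient who stops from dyspnea or fatigue still qualifies. The documents also describe the population as low functioning with severely reduced peak VO2. The lower rows of the table are therefore illustrations, not predictions.

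Finally, the 0.5-point threshold may look impossible with whole-number scores. It is impossible for one person's change, but a difference between group means can be 0.5, and that is what ANCOVA estimates. There is no error there.

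**Conclusion.** The point holds as an inexpensive improvement to a supportive outcome. As written, the plan describes only capped component scores for two quantities that it measures continuously. Against 80% power on the continuous measure, a component score has about 62-66% if 10-20% of patients start at the top and 45-53% if half do. These figures rest on an assumed correlation of 0.75, a common gain between 0 and 0.3 SD, and a normal underlying measure. The share at the top is unknown, so the true size of the loss cannot be fixed from the documents, but a material loss appears even with few patients at the cap. The primary and secondary hypotheses are untouched, and nothing here shows that the 0-12 total is unsuitable or should lose its place as a tested outcome.

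**What to change.** In the SPPB paragraph, state that 4-m gait speed (m/s) and chair-rise rate (stands per second, set to 0 for those unable to complete) are analysed as continuous component endpoints by the planned ANCOVA with baseline value, age and gender. Using a rate keeps patients who cannot finish the task in the analysis, which a completion time would not. Keep the 0-12 total as an analysed outcome, since the cited thresholds for meaningful change apply to it and it allows comparison with other trials. Report by arm the baseline percentage at the maximum score, so that readers can judge whether a ceiling was present.

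The cost is two more exploratory comparisons, to be labelled as such, and a small amount of extra analysis. No visit or test is added, because speed and time are already needed to assign the scores.

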However, RT has never been tested with CR in any type of HF. Furthermore, there are few data regarding RT in HFpEF; a pilot study used a small dose of RT in combination with AT,(58) and another small study included just 3 HFpEF patients.(177) Although initial concerns have been largely allayed regarding the potential effect of RT on left ventricular (LV) function in HFpEF,(135) there remains equipoise in HFpEF. RT can significantly increase arterial stiffness

and LV hypertrophy(153; 225) a potential concern in HFpEF patients who often already have increased arterial stiffness and LV hypertrophy.(106; 124; 137; 230) Therefore, it is important to rigorously test the efficacy and safety of adding RT to CR+AT, as we propose here using state-of-the-art methods.

Objectives

The **primary** aim is to conduct a randomized, controlled, single-blinded 20-week intervention trial of RT added to CR+AT in 84 overweight / obese (BMI \geq 28 kg/m²), older (age \geq 60 years) HFpEF patients to test the following primary hypothesis:

- **The addition of resistance training to CR+AT will improve peak VO₂.**

The **secondary** aims of the study are to test the following secondary hypotheses:

- **Resistance training added to CR+AT will improve retention of skeletal muscle mass.**
- **Resistance training added to CR+AT will improve skeletal muscle mitochondrial function.**
- **The improvement in peak VO₂ with RT will be related to improved skeletal muscle mass and mitochondrial function, and accompanied by improved QOL.**

Peak VO₂ (ml/min) will be assessed by expired gas analysis. Skeletal muscle mass will be measured as thigh muscle area by MRI and total lean mass by DXA.(94; 100) Mitochondrial function and indices of cell death will be assessed by respirometry, protein expression analyses, and enzyme activity assays.(23; 24; 209) QOL will be assessed by the KCCQ instrument. Muscle strength and quality, and cardiac and vascular function will also be assessed.

Methods and Measures

Design

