Thigh muscle tissue will be obtained as previously described from the left *vastus lateralis* by percutaneous needle biopsy under local anesthesia using aseptic technique and a 6mm University College Hospital needle and a 60cc syringe for suction. Over 700 muscle biopsies have been performed using this technique in older research participants, including HFpEF, with good tissue yields (161±79 mg, >100 mg in 83%) and no serious complications.(164) The portion intended for immunoblot analyses is harvested and immediately stored at -80°C. The portion intended for respirometry will be processed as described below.

Mitochondrial function will be examined comprehensively by analysis of key aspects of mitochondrial physiology (**Table 2**). Measures for this exploratory aim were selected to be relevant to older, obese patients with HFpEF and the effects of RT.

Mitochondrial Physiology	Table 2. Mitochondrial Outcome Assessments
Respiratory Function	
 Respiratory control assessed with complex I, II and β-oxidation specific substrates (isolated mitos) Respirometric kinetics and OXPHOS efficiency (Permeabilized muscle fiber bundles- PmFBs)
Content / Structure / Biogenesis	
 Content - citrate synthase activity; Expression of Porin, cardiolipin, Cox4, and Complexes I-V (Western blot); mitochondrial isolation yields Structure – fiber type, cross-sectional area (histology); Mfn1, Mfn2, MFF, DRP1, Fis1, OPA1 expression (Western blot) Biogenesis - PGC1α, TFAM, SIRT3 expression (Western blot)
Mitochondrial-Mediated Cell Death	
 Bcl-2, Bax, ICE, p53, Fas receptor protein, and Cyclophilin D expression (Western blot) Susceptibility to calcium-induced mPTP opening (PmFBs) Mitochondrial H₂O₂ emitting potential (PmFBs)

Muscle biopsy yield in our preliminary studies in HFpEF averaged 138 mg, sufficient for completion of all proposed experiments; 20-30 mg of tissue to isolate mitochondria,(24) 10-15 mg to prepare permeabilized fiber bundles (PmFB)(6), and the remainder (~100 mg) frozen for protein expression/histochemistry.

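### The partial correlations of changes adjust for age and gender but not treatment arm, so they mix the within-arm association with RT's separate effects on the two outcomes

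*Combined protocol and SAP*

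**What the plan says.** The third secondary hypothesis (Objectives) is that the gain in peak VO₂ "with RT will be related to improved skeletal muscle mass and mitochondrial function, and accompanied by improved QOL". The only analysis given for the first part of that statement is one sentence at the end of the Analytical Plan: "Partial correlation analysis adjusting for age and gender will be done to correlate changes in peak" VO₂. The same sentence names what these changes are to be set against: "other key outcomes of interest (muscle mass, mitochondrial function, and QOL"). The QOL part also has an ANCOVA, because "Similar analyses will be done for the secondary outcomes, skeletal muscle mass and mitochondrial function, QOL, and other outcomes".

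The Sample Size section puts power at 80% for these analyses, which are meant to "detect partial correlations as low as 0.30 at the 0.05 two-sided level of significance to examine independent relationships with peak" VO₂.

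The document nowhere adds arm to these correlations, and it plans no arm-specific correlations, interaction or mediation analysis. It does not say in words that the arms are pooled.

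**The concern.** When arm shifts both variables and is left out, patients in the RT arm tend to sit high on both and patients in the other arm low on both. That alone produces a positive correlation, even if patients within an arm who kept more muscle gained no more peak VO₂ than the others. That component restates the two ANCOVA results.

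A reader could take the coefficient as evidence that the patients who kept muscle were those who gained exercise capacity. The Sample Size section speaks of independent relationships, but with this covariate list they can be independent only of age and gender. A real negative within-arm association could also be masked.

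**Working it through.** **Does the plan pool the arms?** Fisher z power for a partial correlation with k covariates is Φ(atanh(r)·√(N − k − 3) − 1.96). With r = 0.30, atanh(r) = 0.3095. With age and gender, k = 2.

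| N | √(N − 5) | Power |
|---|---|---|
| 84 (all randomized) | 8.888 | 78.6% |
| 76 (all evaluable) | 8.426 | 74.2% |
| 42 (one arm, randomized) | 6.083 | 46.9% |
| 38 (one arm, evaluable) | 5.745 | 42.8% |

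The stated 80% is approached only with both arms together, so pooling is a firm inference.

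**Inputs, all from Sample Size.**
- Peak VO₂: difference 82.0 ml/min, root mean square error 107.5, so d₁ = 82.0/107.5 = 0.763.
- Thigh muscle area: difference 3.9 cm², and the "square root of the mean square error was 5.98 using analysis of covariance", so d₂ = 3.9/5.98 = 0.652.
- RCR: the pilot rose "from 2.78 to 7.23 (160% increase; mean square error of 6.372"). The design effect is 60% of 2.78 = 1.668. Read as a variance, 6.372 gives an SD of 2.524 and d = 0.661. Power at 38 per arm is then 81%, which agrees with the stated 80%. Read as an SD, it gives d = 0.262 and 20% power.

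The documents give no SDs of change, so the ANCOVA root mean square errors stand in for them. They state no KCCQ SD, so no QOL figure is possible.

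**Formula.** For 1:1 arms and within-arm correlation r_w, the correlation without arm is

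r = (r_w + d₁d₂/4) / √[(1 + d₁²/4)(1 + d₂²/4)].

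For peak VO₂ with thigh area, d₁d₂/4 = 0.1244 and the denominator is √(1.1455 × 1.1063) = 1.1257.

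- r_w = 0: 0.1244/1.1257 = 0.110
- r_w = 0.30: 0.4244/1.1257 = 0.377
- r_w = −0.30: −0.1756/1.1257 = −0.156
- r_w = 0.30, RT moves only peak VO₂: 0.30/√1.1455 = 0.280
- r_w = 0.30, RT moves only muscle: 0.30/√1.1063 = 0.285

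**Simulation.** 100,000 trials per scenario, 38 per arm, age and gender partialled out, peak VO₂ with thigh area:

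| Scenario | Mean r | Share with p < 0.05 |
|---|---|---|
| r_w = 0, full effects | 0.112 | 15.7% |
| r_w = 0, SDs × 1.25 | 0.074 | 9.5% |
| r_w = 0, 75% of both effects | 0.065 | 8.4% |
| r_w = 0, SDs × 1.5 | 0.053 | 7.3% |
| r_w = 0, 50% of both effects | 0.030 | 5.9% |
| r_w = 0, RT moves peak VO₂ only | −0.001 | 5.2% |
| r_w = 0, RT moves muscle only | 0.000 | 5.1% |
| r_w = 0, full effects, **arm added** | 0.000 | 5.1% |
| r_w = 0.30, full effects | 0.376 | 92.2% |
| r_w = 0.30, full effects, **arm added** | 0.298 | 74.0% |
| r_w = −0.30, full effects | −0.153 | 25.7% |
| r_w = −0.30, full effects, **arm added** | −0.299 | 74.1% |

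A separate simulation of the first scenario with 20,000 trials gave 0.113 and 16.3%.

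For RCR at +60% with r_w = 0, the mean is 0.114 with 16.1% rejection if 6.372 is a variance, and 0.046 with 6.8% if it is an SD.

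**The case against.** The strongest reply is that the hypothesis concerns improvement brought about by RT. Conditioning on arm removes the mean shift between arms, which is the only randomized, RT-driven part of the covariation. What is left is covariation within arms, half of it from patients who had no RT. So the arm-adjusted correlation is not a direct test of the hypothesis either, and the pooled one answers a legitimate descriptive question. This stands in part. Neither version establishes mediation, and adjusting for arm changes the question. But a single coefficient without arm cannot separate the two components, and the ANCOVAs already report the arm differences. This is why both correlations should be shown.

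The second reply is that the 15–16% figure stacks assumptions: full effects on both outcomes, zero within-arm correlation, and residual SDs that are normally no larger than SDs of change. That is right, and the figure should be read as the top of the range for these design effects. Under the positive within-arm association that the Background leads one to expect, 0.30 becomes 0.38 at full effects, about 0.35 at 75% and 0.32 at half. The sign does not change, and the shift lies inside the 95% interval of about 0.08 to 0.49 around r = 0.30 at N = 76. But this bias is systematic, and the interval does not allow for it.

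Third, the sentence says changes in peak VO₂ but does not repeat the word for the other variables. The hypothesis speaks of improved muscle mass and mitochondrial function, so change on change is the natural reading. The wording should say so.

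**Conclusion.** The concern holds. As written, the only analysis of whether the peak VO₂ gain is related to muscle mass and mitochondrial function combines two different things. If RT works on both outcomes, as the plan expects, a zero within-arm association is shifted by up to about 0.11 at the design effects, and an association of 0.30 is inflated to as much as 0.38. If RT moves only one outcome, zero stays zero and 0.30 is slightly attenuated to about 0.28.

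These sizes rest on 76 evaluable patients, on pooled arms (inferred from the power figure), and on root mean square errors used as SDs of change.

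The analysis is supportive, and the Outcome Measure(s) section itself describes the mitochondrial part in exploratory terms: "Measures for this exploratory aim were selected to be relevant to older, obese patients with HFpEF and the effects of RT". The primary and secondary ANCOVAs are untouched. This is a cheap improvement that should be made; it does not threaten the main result.

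**What to change.** In the Analytical Plan, replace the sentence on partial correlations with wording such as: *Changes in peak VO₂ will be correlated with changes in muscle mass, mitochondrial function and QOL across both arms, using partial correlations adjusted for randomized arm, age and gender.*

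Report the correlation adjusted only for age and gender beside it, labelled as including the between-arm difference. Word the conclusion as association, not mechanism, because covariation within arms can still reflect adherence or effort.

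The cost is one phrase and one degree of freedom; arm is already recorded. At N = 76 the Fisher z term changes from √71 to √70, and power for r = 0.30 goes from 74.2% to 73.6%.
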